### **b. Study endpoints**

The primary study endpoint is feasibility and acceptability of the intervention at the end of the trial (6 months post-baseline; see Table 1 for more information).

### **c. Statistical methods**

**Aim 1.** I will calculate frequencies and proportions to assess feasibility outcomes, and means and standard deviations or medians and interquartile ranges to assess acceptability ratings. T-tests or chi-square tests will be used to compare eligible patients who did and did not enroll in terms of demographic and clinical variables, and feasibility and acceptability across enrolled patients based on gender, and medical/psychiatric factors. I will use independent samples t-tests to compare adherent and non-adherent participants from each group on baseline depression and clinical and demographic variables. Exit interviews will be audio recorded, transcribed, and iteratively analyzed using thematic content analysis. Approximately 2-3 members of the study team will review the transcripts to identify common themes and develop a coding framework. We will review our results for agreement and comparison to the raw data, and resolve discrepancies

through discussion with [name] until. All transcripts will be coded according to the coding framework.

**Aim 2. Exploratory outcomes.** As a pilot feasibility trial, I will explore within-group changes in emotional, physiological, and health behavior variables from before to after the intervention. I will examine frequency distributions for all variables and use non-parametric tests if needed. I plan to use linear mixed effects models with repeated measures and an unstructured covariance matrix to assess changes within the MBCT and control group for the following dependent variables: depression symptoms, inflammation, emotion regulation, pro-sociality, health behaviors, and cardiac health (Table 2). The predictor variables will be time (fixed effect; two levels: baseline, post-intervention) and covariates relevant for each dependent variable (random effects; section 5.1). I will explore follow-up outcomes in separate models where time is a fixed effect (three levels: baseline, post-intervention, follow-up) and covariates are included as random effects, with pairwise comparisons between follow-up and the other two time-points. I will explore correlations between changes (post-intervention minus baseline) in depression symptoms and inflammation, emotion regulation, pro-sociality, and health behaviors. For dropouts, I will impute missing data using maximum likelihood estimation and, as a sensitivity analysis, the last observation carried forward. For all analyses, trends will be considered based on a two-tailed  $\alpha=.10$ .

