**Mindfulness-Based Cognitive Therapy (MBCT) could improve depression and cardiac health for ACS patients.** MBCT is an 8-week manualized group intervention that combines CBT with mindfulness meditation to treat depression; it is as effective as antidepressant medication for relapse prevention and reduces symptoms in active depression. The American Heart Association (AHA) recently highlighted the potential benefits of meditation for cardiac health and the need for

further research in this area. Indeed, through the addition of mindfulness training, MBCT could improve both depression and cardiac health. First, mindfulness meditation can reduce levels of CRP, IL-6, and TNF- $\alpha$ , which reduces depression symptoms and benefits cardiac health. Second, meditation increases pro-sociality (e.g., compassion, altruism) and social support, both of which reduce depression symptoms. Given that social isolation is an independent risk factor for ACS mortality and pro-sociality improves cardiovascular functioning, social improvements could have direct benefits on cardiac health. Next, MBCT improves emotion regulation (e.g., rumination about a recurrent event, acceptance of lifestyle changes), which is a key treatment target for depression. Lastly, mindfulness training improves cardiac health behaviors, likely by improving emotional outcomes. Improvements in depression also lead to further improvements in inflammation and pro-sociality to further promote cardiac health.

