## II. SPECIFIC AIMS

- a. Aim 1:** To establish, in a pilot RCT (approx. N=50 participants) with a time- and attention-matched health enhancement control, (a) the feasibility of the recruitment procedures (screening, eligibility, enrollment rates), and feasibility and acceptability of the (b) MBCT and control interventions (adherence, retention, fidelity, satisfaction, group videoconferencing delivery) and (c) data collection procedures by group (adherence, satisfaction). Hypothesis 1a: Recruitment will be feasible as evidenced by screening, eligibility, and enrollment rates; (1b) the MBCT and control interventions and (1c) data collection procedures in both groups will be feasible and acceptable.
- b. Aim 2 (exploratory):** To explore within-group changes in psychosocial and physical health outcomes following virtual MBCT and the control intervention (e.g., depression, inflammation, emotion regulation, pro-sociality, and health behaviors).

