#### *Health Enhancement Control Group*

The control intervention will be a group videoconferencing program focused on depression and cardiac health education (e.g., relationship between depression and cardiac health, cardiac risk factors, cardiac health behaviors, finding resources for mental health care). It will follow the same structure as MBCT but will not contain mindfulness practices or psychoeducation. Participants randomized to the health enhancement control group will be expected to participate in 8-weekly virtual sessions, where each session will last approximately 1.5 hours. To promote equivalent between-session practice, participants will identify health behavior goals to work on and track over the week. A licensed clinician or pre-doctoral or post-doctoral fellow with supervision from a licensed clinician will lead the control group.

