#### *Survey measures*

The self-report survey measures will be the same for the MBCT and control groups. The surveys will be administered within approximately 1-2 weeks before and after the intervention and at 3 months post-intervention. This battery will include the following validated self-report surveys: Assessment of Survivor Concerns (fear of recurrence), CAMS-R (mindfulness), Cardiac History and Symptoms, Current Experiences Scale (CES; resiliency), COVID items,

demographic questionnaire, Expectancy Questionnaire, Experiences Questionnaire (decentering), Group cohesion scale, Hospital Anxiety and Depression Scale (HADS; depression and anxiety), Interpersonal Reactivity Index (IRI; empathy), MAIA-2 body subscales (interoception), MBCT-AS Checklist (fidelity checklist), PHQ-9 (depression), Medical Outcomes Study – Specific Adherence Scale (MOS-SAS; health behaviors), one item from the Short Form-12 (SF-12), Self-Other Four Immeasurables (SOFI; self and other compassion), PROMIS Physical Function (PROMIS-PF; physical function), and The Positive and Negative Affect Schedule-Positive Affect (PANAS-PA). The post-intervention survey will also include a group cohesiveness measures to assess perceived connection with other group members as well as intervention satisfaction questions to assess acceptability. The 3-month follow-up survey will include questions about continued mindfulness practice. The baseline survey, post-intervention survey and post-intervention survey will all include questions related to COVID-19. All three survey batteries are included in the IRB submission.

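### Both arms are delivered in videoconference groups, but the Aim 2 within-arm models allow only for correlation within a person; if changes correlate within delivery groups, intervals are too narrow and the .10 trend threshold is exceeded

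*Combined protocol and SAP*

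**What the plan says.** **Delivery.** The background (section I.a) describes the experimental treatment this way: "MBCT is an 8-week manualized group intervention that combines CBT with mindfulness meditation to treat depression". Aim 1 (section II) lists the delivery features to be assessed for both arms: "MBCT and control interventions (adherence, retention, fidelity, satisfaction, group videoconferencing delivery". Section V.a says of the comparator: "The control intervention will be a group videoconferencing program focused on depression and cardiac health education". Both arms have eight weekly sessions of about 1.5 hours. The post-intervention survey includes a group cohesiveness measure to "assess perceived connection with other group members".

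**Analysis.** Section VI.c, Aim 2, plans "linear mixed effects models with repeated measures and an unstructured covariance matrix" to assess change within the MBCT arm and within the control arm. The terms are given as follows: "The predictor variables will be time (fixed effect; two levels: baseline, post-intervention"; and "covariates relevant for each dependent variable (random effects; section 5.1". Separate follow-up models use three time points. Trends are judged at a two-tailed alpha of .10.

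**What is absent.** No section names a term for delivery group, cohort or interventionist, a cluster-robust standard error, an ICC, a group size or a number of groups. The section 5.1 cited for covariates is not in the document.

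**The concern.** People who share eight weeks of sessions with the same peers may change in similar ways. The protocol's own rationale points that way. Sections I.a and I.b treat social support as one route to lower depression, and they favour live groups over self-guided websites partly because websites lose peer contact. Individual randomization does not prevent correlation that arises during treatment.

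An unstructured covariance matrix over time handles the correlation between one person's repeated measurements. It does nothing for correlation between different people in the same group. If that correlation is positive, the model credits each arm with more independent information than it has. Intervals for the within-arm changes come out too narrow, and changes are called trends more often than the stated .10 implies. The error then runs in the favourable direction, across all the Table 2 outcomes and in both arms.

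**Working it through.** **Starting figures.** Section VI.d gives N=40 without a power analysis, so there is no power figure to reproduce. The only stated error rate is the two-tailed .10 in section VI.c, whose normal critical value is 1.645. With no clustering, 2 × [1 − Φ(1.645)] = .100, which matches the plan.

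**Inputs from the document.** Allocation is 1:1 (section IV.c), so N=40 gives 20 per arm. Aim 1 says about 50, which would give 25 per arm. The two totals need reconciling, but the argument is the same under either.

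**Assumptions.** Group size m is 5 to 10. The ICC is .02, .05 or .10, and it is the ICC of change scores, not of outcome levels. None of these values is in the document.

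**Formulas.**
- Design effect: DE = 1 + (m − 1) × ICC.
- Ratio of true to reported standard error: √DE.
- Actual two-sided error at nominal .10: 2 × [1 − Φ(1.645/√DE)].
- Effective number per arm: 20/DE.

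**Worked case, ICC .05.**
- m = 5: DE = 1 + 4 × .05 = 1.20; √DE = 1.095; 1.645/1.095 = 1.502; error = .133; effective n = 20/1.20 = 16.7.
- m = 10: DE = 1 + 9 × .05 = 1.45; √DE = 1.204; 1.645/1.204 = 1.366; error = .172; effective n = 20/1.45 = 13.8.

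| ICC of change | m | DE | SE ratio | Actual error | Effective n of 20 |
|---|---|---|---|---|---|
| 0 | any | 1.00 | 1.00 | .100 | 20.0 |
| .02 | 5 | 1.08 | 1.04 | .113 | 18.5 |
| .02 | 10 | 1.18 | 1.09 | .130 | 16.9 |
| .05 | 5 | 1.20 | 1.10 | .133 | 16.7 |
| .05 | 10 | 1.45 | 1.20 | .172 | 13.8 |
| .10 | 5 | 1.40 | 1.18 | .164 | 14.3 |
| .10 | 10 | 1.90 | 1.38 | .233 | 10.5 |

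**Check by simulation.** A within-arm t-test on change scores was simulated with 50,000 runs per setting. With complete data and no covariates, this is equivalent to the planned two-time-point model. At ICC .05 the error was .133 with four groups of 5 and .170 with two groups of 10. At ICC .10 it was .167 and .238. At ICC 0 it was .101 and .099.

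**How well could clustering be estimated?** Testing on group means brought the error back to about .10 in the same simulations. But the critical t rises from about 1.7 to 2.13 with five groups per arm, 2.35 with four, 2.92 with three and 6.31 with two. With one group per arm, clustering cannot be estimated at all.

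The group variance itself is poorly determined. In a balanced one-way layout with true ICC .05, its estimate is at or below zero when the F ratio is 1 or less. F is distributed as [1 + m × .05/.95] times a central F on k − 1 and k(m − 1) degrees of freedom, where k is the number of groups. The probability of F ≤ 1 is .48 for four groups of 5, .50 for three groups of 7 and .57 for two groups of 10. At the expected F, the 95% interval for the ICC is about −.16 to .77 for four groups of 5 and −.08 to .99 for two groups of 10.

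**The case against.** The strongest reply is that little rests on these tests. Aim 2 is labelled exploratory, the .10 threshold is deliberately lenient, and no success rule or progression decision uses an Aim 2 p-value. The primary outcomes are the Table 1 benchmarks for feasibility and acceptability, which this point does not touch. That is correct and limits the weight of the point. It does not remove it, because the plan still calls trends at a stated error rate.

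The second reply is that a random group effect hardly helps at this size. That also stands. With two to four groups per arm the variance is estimated at or below zero about half the time, and the model then reverts essentially to the planned one. The dependable part of the remedy is therefore the sensitivity interval at fixed ICC values.

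The third reply is that the missing section 5.1 might list a group term. That cannot be excluded. However, the text describes covariates chosen for each outcome, which is not how one would describe delivery group.

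A reader might infer three stronger things that the documents do not support:
- **That the standard errors are certainly too small.** This needs a positive ICC of change, and no ICC is given.
- **That a comparison between arms is compromised.** Aim 2 concerns change within each arm, and the stated model has no arm or arm-by-time term.
- **That the pilot should supply an ICC for planning the later efficacy trial.** The aims do not include this, and an interval of roughly −.16 to .77 could not plan a trial.

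**Conclusion.** The point holds in conditional form. Both arms are group-delivered, and the Aim 2 models as described have no allowance for it. For any positive ICC of change the within-arm intervals are too narrow and the stated .10 is exceeded. Over the assumed range the reported standard error would need multiplying by 1.04 to 1.38, which is a modest to moderate understatement. The direction is firm once the ICC is positive; the size is not, because group size, number of groups and ICC are all assumed. The consequence is confined to how firmly the exploratory within-arm changes can be described.

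**What to change.** 1. Record each participant's delivery group, and state the planned number and size of groups per arm.
2. Keep the planned model. For every Aim 2 change, add a sensitivity row with the standard error multiplied by √DE at ICC .02, .05 and .10, using the actual group sizes. Show it whatever the estimated group variance, not only when that estimate is zero.
3. Where an arm has at least about three or four groups, also fit a random group effect on the post-baseline measurements, with Kenward-Roger or Satterthwaite degrees of freedom.
4. Describe a change as a trend only with this sensitivity result beside it.
5. Report any ICC with its interval as descriptive, not as a planning value.
6. Supply the covariate list now cited as section 5.1, so that it is clear whether a group term was intended.

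The cost is one recorded variable, a few extra rows per outcome and, where feasible, one extra model. Trial conduct is otherwise unchanged. The price in the results is wider intervals and a group variance that will be poorly estimated.

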## VI. BIOSTATISTICAL ANALYSIS

### a. Specific data variables being collected for the study

The primary outcomes are feasibility and acceptability of the intervention and research procedures (Table 1). Study staff will record all feasibility outcomes throughout recruitment, screening, enrollment, and the intervention, data collection, and follow-up phases.

Table 1. PRIMARY OUTCOMES	
Feasibility	
Recruitment	$\geq 70\%$ consent to screening; $\geq 70\%$ meet screening criteria; $\geq 70\%$ of eligible enroll; enroll $\geq 20$ participants/month
Eligibility criteria	$< 20\%$ ineligible due to each criterion; reasons for ineligibility; reasons for refusal; characteristics of refusers
MBCT and control interventions	Adherence: $\geq 75\%$ session attendance; retention: $\geq 75\%$ post-assessments, $\geq 70\%$ follow-up assessments completed; fidelity: checklist score $\geq 80\%$ ; $\geq 75\%$ complete home practice at least 3 days/week
Videoconferencing	$< 20\%$ of connections dropped during session; $< 20\%$ of sessions missed due to technical problems; number ( $M < 2.0$ ) and type of problems; $< 20\%$ ask for extra training, type of extra training needed
Blood spots	Adherence: $\geq 75\%$ submitted at baseline, post-intervention, $\geq 60\%$ submitted at follow-up; 80% adequate quality
Acceptability	
MBCT and control interventions	Session satisfaction and helpfulness, enjoyment, relevance, utility of each session component (1=not at all, 10=very much; $M \geq 7.5$ ; post-session survey ); overall program satisfaction ( $M \geq 7.5$ ), $\geq 75\%$ plan to use the skills, $\geq 75\%$ would recommend the program to others ( post-intervention )

	survey); likes, dislikes, suggestions for improvement (exit interview); <math>\geq 60\%</math> continue meditation practice (follow-up survey)
Videoconferencing	Ease and confidence of use (1=not at all, 10=extremely <math>M \geq 7.5</math>), interference of technical problems (1=none, 10=extreme; <math>M < 2.0</math>), audiovisual quality and overall satisfaction (1=poor, 10=excellent; <math>M > 7.5</math>; post-session survey); pros and cons, suggestions for improvement (exit interview)

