## **VII. RISKS AND DISCOMFORTS**

**a. Complications of surgical and non-surgical procedures**

There are no surgical procedures as part of this study. Given that participants do not need to physically come to the hospital to participate in any study procedures, there is no risk of physical injury to participants.

The process of collecting a dried blood spot sample is relatively painless and non-invasive; however, participants may face minimal discomfort when completing this procedure. Prior to the dried blood spot sample collection, participants will be informed that the procedure may involve mild, temporary pain at the finger prick site and will be provided with suggestions for minimizing any pain that is bothersome (e.g., putting ice on the site). Participants will be sufficiently trained by study staff in how to self-collect their blood samples at home. Participants will be given the option to opt out of any dried blood spot collection points, for any reason. Participants who oppose the provision of dried blood samples will not be

excluded from additional study procedures. In our previous study, it was common for ACS patients to already have experience using the blood spot finger-prick technique for their healthcare and almost all participants expressed comfort and willingness to complete this procedure as part of a research study.

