## **IX. MONITORING AND QUALITY ASSURANCE**

**a. Independent monitoring of source data**

Source materials will include information collected from survey questionnaires at baseline, post-intervention, and 3-month follow-up; exit interviews; weekly practice logs; post-session surveys; and blood spot collection procedures. All self-

report questionnaires will be entered electronically via REDCap. Individual exit interviews will be conducted by phone or videoconferencing. Upon their receipt, all dried blood spot samples will be stored securely in an MGH affiliated lab, on the MGH campus. Samples will later be shipped, in accordance with MGB and CDC guidelines, to our collaborators [name] and [name] at Northwestern University for storage and/or processing. All samples will be labeled with the patient ID, date of collection, group assignment, and time point (baseline, post-intervention, 3-month follow-up). We will follow all CDC shipping guidelines (e.g., placing a freeze pack inside of an insulated shipping container, placing sealed plastic bags containing the samples into a box). We will seal the box tightly with tape and ship specimens via courier to [name] in Health Lab at the Northwestern University Feinberg School of Medicine.

[name] will securely store the samples in his locked lab at Northwestern before bringing them for processing to his collaborator [name] at the Laboratory for Human Biology Research at Northwestern University. The blood samples will not contain identifiers that could be used by the outside collaborators to link the data to individual subjects; they will be labeled with participants' study ID numbers and not any personally-identifying information, and only Partner's study staff will have access to the data file linking participant's personal information to their study ID number. Study staff have completed CDC and HealthStream trainings on dried blood spot storage and shipping and have acquired the proper documentation to ship samples to a non-MGB lab.

All information collected will be for the purposes of research and will only be accessible to study staff and stored securely on the Partners' network. Survey and practice log data will be reviewed for completeness though participants will be allowed to skip any questions they are not comfortable answering.

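### Aim 2's only missing-data sensitivity analysis is last observation carried forward, which in the baseline/post model nearly reproduces the completers-only test result; both Aim 2 models also enter covariates as random effects.

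*Combined protocol and SAP*

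**What the plan says.** Section VI.c (Statistical methods, Aim 2) plans linear mixed models of change within each arm. One model has baseline and post-intervention; a separate one adds the 3-month follow-up. For dropouts it states: "I will impute missing data using maximum likelihood estimation and, as a sensitivity analysis, the last observation carried forward". Across all Aim 2 analyses, "trends will be considered based on a two-tailed" alpha of .10. The document describes no other sensitivity analysis for missing data.

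The first model includes "covariates relevant for each dependent variable (random effects; section 5.1"). In the follow-up model "covariates are included as random effects, with pairwise comparisons between follow-up and the other two time-points". The document is numbered I to X with lettered subsections and has no section 5.1, so the covariates are not identified for any outcome.

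Table 1 (section VI.a) shows how much missing data the plan would accept. The survey benchmark is "retention: $\geq 75\%$ post-assessments, $\geq 70\%$ follow-up assessments completed". For blood spots it is at least 75% at baseline and post-intervention, then at least 60% "submitted at follow-up; 80% adequate quality". Patients who stay in the trial can also have missing values: "Participants will be given the option to opt out of any dried blood spot collection points, for any reason" (section VII.a), and "participants will be allowed to skip any questions they are not comfortable answering" (section IX.a). The missing-data rule mentions dropouts only.

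**The concern.** A sensitivity analysis should show how far a conclusion moves as the assumption about the unseen values changes. LOCF examines one point, no change and no spread. If its test result is close to determined by the completers' data, a trend that survives LOCF may be called robust although little has been tested. The risk is greatest when patients who do badly are the ones who leave. Section VIII.b says the pilot will inform a later efficacy trial, so an over-confident reading of an Aim 2 trend could be carried forward. Separately, a covariate described as adjusted for may not adjust the mean at all if it enters only as a random effect.

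**Working it through.** The plan gives no figure to reproduce: section VI.d states that no power analysis was done.

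**Inputs from the document.** Retention r = 0.75 post-intervention and 0.70 at follow-up (Table 1); alpha .10 two-tailed (VI.c); 1:1 allocation (IV.c); N = 40 (VI.d) or about 50 (II, Aim 1), so 20 or 25 per arm; d = 0.35 to 0.61 for depression (I.b), assumed here to apply to within-group change divided by its SD. **Assumed:** normal scores, correlation between visits 0.3 to 0.7, no covariates in the simulations, and the dropout mechanisms.

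**Baseline/post model.** Let completers have mean change m and SD s, with retention r of n patients. LOCF adds zeros, so

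- mean = r·m
- variance of the mean = [r·s² + r(1 − r)·m²]/n
- t(LOCF) = t(completers)/√(1 + (1 − r)(m/s)²)

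At r = 0.75, for m/s = 0.2, 0.5 and 0.8:

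- 1/√(1 + 0.25×0.04) = 0.995
- 1/√(1 + 0.25×0.25) = 0.970
- 1/√(1 + 0.25×0.64) = 0.928

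The padded sample also has more degrees of freedom, which offsets this small loss. Exact paired t results:

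| Per arm (completers) | m/s | Completers t, p | LOCF t, p |
|---|---|---|---|
| 20 (15) | 0.35 | 1.36, 0.197 | 1.35, 0.194 |
| 20 (15) | 0.50 | 1.94, 0.073 | 1.89, 0.074 |
| 20 (15) | 0.61 | 2.36, 0.033 | 2.27, 0.035 |
| 25 (19) | 0.61 | 2.66, 0.016 | 2.56, 0.017 |

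The estimate does move: 0.75×0.61 = 0.46.

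**Simulated verdicts** (at least 20,000 replicates per scenario). LOCF and completers agreed at .10 in over 99.9% of trials, both under random dropout and when poor responders dropped out. With no true change, poor responders leaving, 20 per arm and correlation 0.5, LOCF and completers each declared a trend in about 34% of trials against a nominal 10%. Maximum likelihood did so in about 26%. LOCF and maximum likelihood verdicts agreed in about 91-97% of trials under random dropout and 88-98% under outcome-related dropout.

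**Follow-up contrasts.** LOCF and completers agreed in about 100% of trials for follow-up versus post-intervention, but in only about 86-96% for follow-up versus baseline, where a post-intervention score may be the one carried.

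**Relapse.** Assume a change of −0.50 SD at post-intervention and −0.25 SD at follow-up, so a true relapse of 0.25.

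- Surveys (25% then 30% missing): post 0.75×(−0.50) = −0.375; follow-up 0.70×(−0.25) + 0.05×(−0.50) = −0.20; apparent relapse 0.175, shortfall 0.075. Of this, 0.25×0.25 = 0.0625 comes from baseline carried forward for patients lost before post-intervention, and 0.05×0.25 = 0.0125 from patients lost later.
- Blood spots (25% then 40% missing): follow-up 0.60×(−0.25) + 0.15×(−0.50) = −0.225; apparent relapse 0.15, shortfall 0.10, made up of 0.0625 and 0.15×0.25 = 0.0375.

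**Blood-spot missingness.** If the 80% quality benchmark applies to submitted samples, usable samples could be 0.75×0.80 = 60% post-intervention and 0.60×0.80 = 48% at follow-up, so 40% and 52% missing. Baseline samples may be missing too, and LOCF has nothing to carry forward for those.

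**Covariates.** With patient-level coding, a random coefficient on xᵢ with variance σ² changes the covariance to Vᵢ = R + σ²xᵢ²J and leaves the mean model unchanged. In a large simulation (n = 200,000, true change −0.50, 25% covariate-related dropout of assumed strength) the estimate was −0.517 to −0.548 with random covariates and −0.496 to −0.501 with fixed. That is a shift of about 0.02-0.05 SD, or 0.1-0.2 of a standard error of 0.255. With complete data and time-constant covariates it is nil.

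**The case against.** The main analysis is maximum likelihood on available data; a completers-only test is not planned. A reader might infer that LOCF simply repeats the planned analysis. It does not: the two disagree in roughly 2-12% of simulated trials, and LOCF also cuts the estimate by a quarter at 75% retention, which a reader would see. This stands, and the near-exact repetition is confined to the completers' test verdict.

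A reader might also hold LOCF's coverage against it. With a true −0.50 SD change and random dropout (20 per arm, correlation 0.5), its 90% interval covers the truth in about 82% of trials. But that setting is one where maximum likelihood is already right, and a sensitivity scenario departs from it on purpose. LOCF's standard error of 0.197 is close to the empirical 0.201 for its own target. For the same reason, the number of trends that a shift analysis removes there does not show that it is the better method. The argument rests on the algebra and on the outcome-related dropout case.

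Another tempting reading is that LOCF hides relapse mainly by copying post-intervention scores. The arithmetic shows that the baseline carried forward accounts for most of the shortfall.

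Finally, Aim 2 is exploratory and within-group, and about five dropouts per arm cannot support firm conclusions under any method. That stands and sets the severity.

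**Conclusion.** The point holds as a minor one. LOCF is the sole sensitivity analysis, it tests one fixed assumption, and for baseline to post-intervention its verdict at .10 adds almost nothing to the completers' verdict, including under outcome-related dropout. It is not reliably conservative: in the no-change case above it found more trends than maximum likelihood (34% against 26%). The t factors follow from algebra at the plan's own retention benchmark. The agreement rates, relapse figures and covariate shift depend on the assumed effects, correlations and dropout mechanisms, and the benchmark missing shares are not forecasts.

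The documents do not support a claim that maximum likelihood is wrong or that Aim 2 is invalid. The covariate term is mis-specified under the usual coding, with little numerical effect. The feasibility and acceptability endpoint in section VI.b is untouched.

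**What to change.** 1. Keep maximum likelihood as the main Aim 2 analysis. For depression and the key inflammatory markers, make the sensitivity analysis delta-adjusted multiple imputation over a short pre-stated range: missing at random, graded shifts toward worse (for example 0.25 and 0.5 SD), and zero change with residual variation retained. LOCF may stay alongside, but not as the only check. Report estimates with 90% intervals side by side, as descriptive results. An example of what this adds: with 15 of 20 completing and equal spread in dropouts, a completers' improvement of 0.61 SD of change loses p < .10 once dropouts worsen on average by about 0.23 SD.
2. State whether the missing-data rule covers opted-out or inadequate blood spots, skipped items and missing baseline samples.
3. In both models, enter baseline covariates as fixed effects with the patient as the repeated unit. Name them for each outcome in place of the section 5.1 reference.

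The cost is SAP wording and modest extra analysis, with no new data or patients. The shift sizes need a brief justification for each scale. Intervals will be wider than LOCF's: in the 20-per-arm simulation with random dropout, the standard error was about 0.26-0.27 SD against 0.20.
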